### Primary outcome variables

The primary outcome will be "definite relapse or probable relapse". Definite relapse will be defined as the occurrence of an episode of illness within the 21-day period after antibiotic completion in which the same organism with similar antibiogram is grown, as in the original episode. Probable relapse will be defined as the occurrence of an episode of illness within 21-day period that is diagnosed to be: Clinical diagnosis of bacterial sepsis, in the setting of a sterile blood culture. Part B of the proforma, along with all investigation reports will be mailed to the nodal center, where a Neonatologist who is unconcerned with the rest of the study, will be asked to adjudicate whether the concerned episode is a relapse or not.

Since this is a non-inferiority trial, the analysis will be done both as per protocol and as per intention to treat. Both the analyses will be reported, bearing in mind that the per protocol analysis is actually the more conservative of the two, with less bias towards "no effect".

In the per protocol analysis, the following subjects will be excluded from analysis:

- a) In the 14-day group: patients whose 8th- 14th day of antibiotics could not be completed for any reason (including, but not limited to non-availability of cannula, a fresh episode of sepsis requiring change of antibiotics, withdrawal of consent or unscheduled discharge),
- b) Subjects in either group whose primary outcome could not be assessed due to loss to follow-up or withdrawal of consent.

In the intention-to-treat analysis, all randomized subjects will be analyzed according to the group to which they were randomized, irrespective of compliance or change of antibiotics due to a fresh episode. Subjects in the 7-day group whose primary outcome could not be assessed due to loss to follow-up or

withdrawal of consent will be assumed to have definite relapse and those in the 14-day group to not have relapse.

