### **Sample Size Calculation**

The sample size was calculated to be 350 in each arm based on the following assumptions: Event rate for the composite primary outcome of "definite or probable relapse" assumed to be 10% (combining both 7- and 14-day treatment arms) based on the earlier study (Chaudhary G, Dutta S, Narang A, Journal of Tropical Pediatrics 2006), non-inferiority margin of 7%, one sided alpha level as 5% and power of 90% and loss to follow- up of approximately 10%.

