# Data analysis

The baseline variables shall be described using descriptive statistics. As all the outcome variables are categorical,  $x^2$  test with Yates correction or Fisher's Exact test as applicable will be used. Sub-group analysis has been planned for the following sub-groups: 1000-1500 g, 1501-2000 g, >2000 g, those infected with gram positive organisms and those with radiological pneumonia. For the sub-group analyses, level of significance will be kept as p< 0.01. Analysis shall be done using the statistical software packages SPSS version 10.

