Title:

Comparison of the Efficacy of a 7-day Versus 14-day Course of Intravenous Antibiotics in the Treatment of Uncomplicated Neonatal Bacterial Sepsis: a Randomized Controlled Noninferiority Trial

NCT number: NCT 03280147

Date of document: 26 September 2019

STATISTICAL ANALYSIS PLAN

The baseline variables shall be described using descriptive statistics. Categorical variables will be described by percentages. Numerical variables will be described as mean (standard deviation) or median (1st, 3rd quartile), depending on distribution. Normality of distribution of numerical variables will be tested by Shapiro Wilk test and QQ plot.

The primary outcome variable is "definite or probable relapse" within 21 days after stopping antibiotics. Secondary outcome variables include individually definite and probable relapse within 21 days and 28 days after stopping antibiotics; definite and probable relapse within 28 days and 35 days after randomization; "definite or probable relapse" within 28 days and 35 days after randomization; secondary bacterial infections within 35 days after randomization and adverse events within 35 days after randomization. Analysis will be both per protocol as well as intention-to-treat, as this is a noninferiority trial.

As all the outcome variables are categorical, chi-square test with Yates correction or Fisher's Exact test, as applicable, will be used to compare the 2 groups.

Sub-group analysis has been planned for the following sub-groups: birth weight 1000-1499 grams, 1500 to 2000 grams, and >2000 grams, those infected with gram positive organisms versus the rest and those with radiological pneumonia versus those without radiological pneumonia. A p-value for the test of interaction (Breslow-Day test) will be derived for the subgroup analyses.

Multi variable logistic regression analysis will be performed to determine the relationship between group membership (7-day course of antibiotics versus 14-day course of antibiotics) and the primary outcome after adjusting for the following baseline covariates: birth weight, age of neonate, infection with gram positive organisms, number of days by which clinical remission of sepsis achieved prior to randomization.

Mid-term analyses will be performed by an independent Data Safety Monitoring Board at 1/3rd and 2/3rd of expected recruitment.

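### The primary outcome is assigned only tests of equality; nothing ties the result to the 7-point non-inferiority margin or says which analysis set must meet it

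*SAP*

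**What the plan says.** The Protocol's Sample Size Calculation fixes the design quantities: 350 per arm from a 10% event rate, with a "non-inferiority margin of 7%, one sided alpha level as 5% and power of 90% and loss to follow- up of approximately 10"%. This is the only place where the margin, the one-sidedness or the alpha appears.

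The analysis sections do not take them up. The Protocol's Data analysis section covers all outcomes with one sentence: a chi-square "test with Yates correction or Fisher's Exact test as applicable will be used". The SAP repeats it: "chi-square test with Yates correction or Fisher's Exact test, as applicable, will be used to compare the 2 groups". The SAP then adds an adjusted model: "Multi variable logistic regression analysis will be performed to determine the relationship between group membership" and the primary outcome, with no margin on any scale.

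On analysis sets, the SAP says "Analysis will be both per protocol as well as intention-to-treat, as this is a noninferiority trial". The Protocol, under Primary outcome variables, says "Both the analyses will be reported, bearing in mind that the per protocol analysis is actually the more conservative of the two". Neither says what happens if the two disagree. The same Protocol section defines the sets. The per-protocol set drops 14-day subjects who did not complete days 8 to 14, one listed reason being "a fresh episode of sepsis requiring change of antibiotics". In the intention-to-treat analysis, 7-day subjects lost to follow-up or "withdrawal of consent will be assumed to have definite relapse and those in the 14-day group to not have relapse".

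**The concern.** A Yates chi-square or Fisher test asks whether the two relapse rates differ at all. A non-significant result is compatible with an excess above 7 points, so it cannot show non-inferiority. The 90% power and 5% alpha claimed for 350 per arm belong to a comparison with the margin, and the analysis sections contain no such comparison.

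The logistic model does not fill the gap, because a 7-point difference has no single odds ratio. It is 1.84 at 17% versus 10% and 2.24 at 13.5% versus 6.5%.

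The open choice of analysis set adds to the problem. As defined, the two sets can behave very differently, so the trial's main conclusion could depend on a choice made after the results are known.

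**Working it through.** **Inputs.** From the Protocol's Sample Size Calculation: event rate 10%, margin 7%, one-sided alpha 5%, power 90%, loss 10%, 350 per arm. Assumed, because the documents give no figure: a true difference of zero for sizing, a two-sided 5% level for the equality test, and the alternative true rates used below.

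**1. The plan's own figure.** n = (z₀.₉₅ + z₀.₉₀)² × 2p(1−p) / margin² = (1.645 + 1.282)² × 2 × 0.10 × 0.90 / 0.07² ≈ 314.6 with unrounded z-values, so 315 evaluable per arm. Then 315 / 0.9 = 350. The stated size is reproduced, and the 7% is therefore an absolute difference.

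**2. Two rules on the same data.** At 315 per arm and a pooled 10%, 63 relapses are expected (630 × 0.10). The margin rule is d + 1.645 × SE < 7 points, with d = p₇ − p₁₄ and SE = √[p₇(1−p₇)/315 + p₁₄(1−p₁₄)/315]. For 38/25, d = 4.13 and SE = 2.385 points, so the limits are 4.13 ± 3.92, or 0.20 to 8.05.

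| 7-day / 14-day relapses | Upper limit of 90% CI, points (Wald / Newcombe / Miettinen-Nurminen) | Excludes 7 points? | Yates p |
|---|---|---|---|
| 36 / 27 | 6.78 / 6.84 / 6.87 | yes | 0.288 |
| 37 / 26 | 7.42 / 7.48 / 7.51 | no | 0.184 |
| 38 / 25 | 8.05 / 8.11 / 8.14 | no | 0.111 |
| 39 / 24 | 8.68 / 8.75 / 8.78 | no | 0.063 |
| 40 / 23 | 9.31 / 9.38 / 9.42 | no | 0.034 |

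The three middle rows show no significant difference, yet do not show non-inferiority.

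**3. How often this happens.** Exact enumeration of two binomials, 315 per arm, Wald limits:

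| True rates, 7-day vs 14-day | P(Yates p ≥ 0.05 and 7 points not excluded) |
|---|---|
| 10% vs 10% | 8.2% |
| 11% vs 9% | 22.2% |
| 12% vs 8% | 30.8% |

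**4. If non-significance were read as success.** The documents do not say this, so it is an illustration. At a true 7-point excess, p ≥ 0.05 occurs 30.6% of the time at 17% vs 10% and 19.3% at 13.5% vs 6.5%. The margin rule passes 5.2% and 5.4% of the time, and its power at 10% vs 10% is 90.0%.

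**5. The converse.** A 7-day arm significantly worse but inside the margin needs a pooled rate of about 5% or less. An example is 22/315 vs 10/315, with Yates p = 0.046 and Wald upper limit 6.68. Its chance is below 1 in a million at 12% vs 8% and 12% at 7% vs 3%.

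**6. Why the deciding set matters.**

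- *Intention-to-treat, 350 per arm, true 10% vs 10%, equal loss L.* The imputation gives expected rates of 0.10(1−L) + L and 0.10(1−L), so the difference shifts by L. At the planned 10% loss this is 19% vs 9%. The chance of passing is 69% at L = 2%, 21% at 5% and 0.3% at 10%. The 2% and 5% losses are illustrative.
- *Per protocol, 315 per arm, 7-day rate 10%.* If the one-sided exclusion lowered the 14-day rate to 9%, 8% or 7% (assumed), the chance of passing would be 82%, 71% or 57% instead of 90%.

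**The case against.** The best defence is that the criterion is planned and only the link is unwritten. Both documents declare non-inferiority, the margin and alpha are stated, and the test sentence is a blanket one covering adverse events too. It nowhere says that p ≥ 0.05 means non-inferiority, so a careful analyst would compute an interval anyway. It stands that the margin, sidedness and alpha are fixed, and that step 4 rests on a reading the documents do not state. But the named test still cannot answer the primary question, and the purpose of a plan is that the answer does not depend on what an analyst later chooses.

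Three further points have some force.

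- The interval method makes little difference. The three methods agree on every split in the table, so naming one is good practice rather than the heart of the matter.
- The Protocol leans towards per protocol by calling it the more conservative analysis. That is a lean, not a rule, and it promises only that both will be reported.
- The direction of the per-protocol effect is not certain. The primary outcome counts episodes after antibiotics are completed, so a fresh episode during days 8 to 14 in the 14-day arm may not be a primary event, and excluding those subjects need not lower that arm's rate. The 82%, 71% and 57% figures are therefore conditional.

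Finally, a test of difference does suit the Protocol's interim rule to stop if failure is significantly higher with 7 days. That rule is not in question here.

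**Conclusion.** The concern holds and must be fixed. The analysis assigned to the primary outcome does not test the hypothesis the trial was sized for, and no rule says which analysis set decides. This follows from the text and needs no assumed rate.

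The size does rest on assumptions: 315 evaluable per arm, a two-sided 5% equality test and the true rates shown. Under these, a non-significant result that leaves 7 points open has a chance of 8% to 31% for true differences of 0 to 4 points around a pooled 10%. The sample size itself is sound for the margin rule in evaluable subjects.

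**What to change.** In the SAP and in the Protocol's Data analysis section, replace the equality test as the final primary analysis with wording such as:

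> The primary analysis is the risk difference (7-day minus 14-day) in the primary outcome with a two-sided 90% confidence interval, equivalent to a one-sided 95% upper limit, by [method named in advance]. Non-inferiority is concluded if the upper limit is below 7 percentage points.

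Also:

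- State, before outcomes are compared by group, whether the per-protocol set, the intention-to-treat set or both must meet the margin. The choice is the team's. It should weigh the exclusion that applies to the 14-day arm only and the imputation that shifts the difference by about the loss rate.
- Report the relapse secondary outcomes (items 1 to 7) as risk differences with confidence intervals, with chi-square or Fisher p-values as supplementary.
- Label the logistic model as supportive.
- If an interim look can claim non-inferiority, adjust the final interval's level to match. Leave the interim harm rule as it is.

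The cost is a few sentences and one decision, with no new data. The planned alpha, margin, 350 per arm and 90% power are kept if a set of evaluable subjects with equal 10% rates decides. If the intention-to-treat analysis with its present imputation must also pass, the 90% no longer applies (step 6), and the team should make that choice knowing this.

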### METHODS

#### Study design

This is a multi-centric, randomized, active-controlled, non-inferiority trial. Stratification of subjects is done according to center and birth weight.

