#### Randomization procedure

Stratified, block randomization will be employed as described above. Randomly varying block sizes will be used and size of the blocks will be concealed until the end of the study. Each block will have equal number of allocations to Group A and Group B in a random sequence. Stratification will be by birth weight (1000-1499, 1500-2000g and >2000 g) and by Centre. Random number lists generated from a website http://randomizer.org will be converted into the sequence of allocation to the 2 Groups. Concealment of allocation

Slips bearing the allocated Group will be placed in opaque envelopes, which will be sealed and numbered serially on the outside. There would be separate sets of such envelopes, one for each stratum (ie Center and birth weight group). In each center, envelopes will be opened in serial order, as each subject is included in the study. The name and identification details of the subject will be written on the outside of each envelope and all envelopes will be returned to the Principal Investigator in the nodal center.

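### Randomisation is blocked by centre and birth weight, but the group comparison is unstratified and no stratified estimate is planned for the 7% margin: valid, with a small and avoidable loss

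*SAP*

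**What the plan says.** - Protocol, Study design: "Stratification of subjects is done according to center and birth weight".
- Protocol, Randomization procedure: "Stratification will be by birth weight (1000-1499, 1500-2000g and >2000 g) and by Centre", and "Each block will have equal number of allocations to Group A and Group B in a random sequence". Each stratum has its own set of envelopes.
- SAP, group comparison: "chi-square test with Yates correction or Fisher's Exact test, as applicable, will be used to compare the 2 groups". Protocol, Data analysis, plans the same tests: "test with Yates correction or Fisher's Exact test as applicable will be used". Neither sentence mentions centre or birth weight.
- Protocol, Sample Size Calculation: "non-inferiority margin of 7%, one sided alpha level as 5% and power of 90" per cent, with a 10% event rate, about 10% loss to follow-up and 350 infants per arm.
- Birth weight appears in the analysis plan as a subgroup factor (with a Breslow-Day test in the SAP) and as a covariate in the SAP's logistic model. Centre appears in no planned analysis. Neither document names a confidence interval, a standard error or a stratified estimate for the primary risk difference.

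**The concern.** Blocking within strata forces the arms to be nearly balanced on centre and birth weight. Differences in relapse risk between strata then add almost nothing to the sampling variation of the difference between arms. An unstratified standard error still counts that between-stratum variation, so it overstates the uncertainty. In a non-inferiority trial the upper confidence limit is what meets or misses the margin, so an interval that is too wide costs some power. The strata are already recorded, so the loss is avoidable. What has to be settled is whether it is large enough to matter.

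**Working it through.** **1. The plan's own figure.** From the protocol: risk 10% in both arms, margin 0.07, one-sided alpha 5%, power 90%, loss 10%.

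n = (1.645 + 1.282)² × 2 × 0.1 × 0.9 / 0.07² ≈ 315 assessed per arm; 315 / 0.9 = 350. This reproduces the stated size. Stratification does not enter the formula.

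**2. Size of the effect by formula.** At 315 per arm the unstratified one-sided 95% half-width is 1.645 × √(2 × 0.09 / 315) = 3.93 points. With blocking, the relevant variance is the mean of p(1−p) within strata, which is 0.09 minus the variance of the stratum risks. For three equal strata averaging 10% (assumed risks):

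| Stratum risks | Within-stratum variance / 0.09 | Half-width, points | Unstratified too wide by |
|---|---|---|---|
| 10/10/10% | 1.000 | 3.93 | 0 |
| 5/10/15% | 0.982 | 3.90 | 0.9% |
| 2/10/18% | 0.953 | 3.84 | 2.5% |
| 4/6/20% | 0.944 | 3.82 | 2.9% |
| 1/5/24% | 0.888 | 3.71 | 6.1% |

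**3. The same formula at the margin.** Take 6.5% versus 13.5%. The two variances sum to 0.065 × 0.935 + 0.135 × 0.865 = 0.1776. Shrink the 5/10/15% pattern in proportion to a 6.5% mean (3.25/6.5/9.75%) and add 7 points throughout in the other arm. The between-stratum variance is then 2 × 0.0325² / 3 = 0.00070 in each arm. The share removed is 2 × 0.00070 / 0.1776 = 0.8% of the variance, or 0.4% of the standard error. That is less than half the excess at equal risks.

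**4. Simulation with sparse strata.** Assumed: 700 randomised, 10% random loss, 6 centres of unequal size, birth-weight mix 25/35/40%, blocks of 4 or 6, 100,000 trials per row. Centre SD is on the logit scale. An unstratified Wald interval is compared with a Mantel-Haenszel risk difference using Sato's variance. Power is at no true difference; type I error is at 6.5% versus 13.5%.

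| Risks by birth weight; centre SD | Unstratified SE / true SD | Half-width, unstratified → stratified | Power, % | Type I error, % |
|---|---|---|---|---|
| No differences | 0.993 | 3.92 → 3.93 | 89.9 → 89.8 | 5.3 / 5.3 |
| 14/10/7%; none | 1.003 | 3.92 → 3.91 | 90.1 → 90.2 | 5.4 / 5.4 |
| 14/10/7%; 0.4 | 1.008 | 3.92 → 3.88 | 90.2 → 90.5 | 5.2 / 5.2 |
| 20/10/5%; 0.4 | 1.017 | 3.92 → 3.83 | 90.4 → 91.2 | 5.3 / 5.5 |
| 20/10/5%; 0.8 (extreme) | 1.038 | 3.92 → 3.74 | 90.8 → 92.2 | 5.1 / 5.4 |

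Monte Carlo error is about 0.2% for the ratio, 0.1 points for power and 0.07 points for type I error. With 5 or 10 centres the picture is the same: type I error stays at 5.0-5.5% for both methods. Repeat simulations with other centre sizes and effects put the ratio at 1.011-1.017 for moderate differences and 1.034-1.039 in the extreme case at equal risks. At a true 7-point difference the ratio was only 1.000-1.013. The true SD of the stratified estimate was 0.994-1.004 times that of the unstratified one.

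**5. Sparsity.** Three bands over 5 to 10 centres give 15 to 30 strata. With 10% of 630 assessed infants, 63 events give 63/30 = 2.1 to 63/15 = 4.2 per stratum. With the 100 events expected in the protocol's section on mid-term analysis, the range is 3.3 to 6.7. At 63 events, 5-30% of strata had no event in simulation.

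**The case against.** The strongest reply is that stratifying buys almost nothing. The estimate itself is no more precise, since the true SDs agree within about 0.6%. The extra power comes from a smaller estimated standard error. Type I error does not move closer to 5%; in the extreme case it rises slightly further above it. The criticised interval is also hypothetical, because the plan names no interval at all. All of this stands, and it is why the point is minor and conditional. The lack of any planned test against the margin is a separate and larger matter.

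What survives is narrower. Once an interval is set against the 7% margin, it should reflect how infants were allocated, and the method should be fixed in advance.

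A reader might also infer three stronger things that the documents do not support:

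- **That ignoring the strata invalidates the comparison or inflates false claims of non-inferiority.** Any error in the standard error from ignoring the strata is towards too wide an interval, and type I error is about the same with either method.
- **That the sample size is wrong.** It is reproduced exactly without reference to strata.
- **That leaving centre out of the logistic model is a fault.** That model already includes birth weight. In simulation with 6 centres, adding centre raised the standard error of the log odds ratio by 0.5-1.4% (4.1% in the extreme case), so leaving it out is defensible.

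**Conclusion.** The point holds as a minor matter of analysis choice. The design stratifies by centre and birth weight, the main comparison uses neither, and no stratified estimate is planned for the margin. At equal true risks an unstratified interval would be about 1-2% too wide for moderate stratum differences, or 0.04-0.09 points of a 3.92-point half-width. In the extreme simulated case it would be 3-4% too wide (0.18 points). At a true 7-point difference the excess is about 0-1%. If strata do not differ in risk, nothing is gained.

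The sizes depend on assumed stratum risks, stratum sizes, centre numbers and block sizes, and on random loss that is equal in the two arms. The formula shows that a wider spread of risks than simulated, such as 1/5/24%, would raise the excess to about 6%. The exclusions from the per-protocol analysis that apply only to the 14-day group were not modelled.

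**What to change.** State in the SAP that the primary risk difference (7-day minus 14-day) will be estimated stratified by centre and the three randomisation birth-weight bands. Specify Mantel-Haenszel weights, a variance suited to sparse strata such as Sato's, and a rule fixed in advance for pooling small centres. Compare the one-sided 95% upper limit with the 7% margin.

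The cost is wording only, since the strata are already recorded. The downsides are:

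- The pooling rule is essential, because strata are sparse on either event count.
- If strata do not differ in risk, about 0.1-0.2 points of power are lost.
- Type I error may rise by up to 0.2-0.3 points in the extreme case.

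One clerical item can be settled at the same time. The birth-weight cut-points under Data analysis in the protocol put an infant of exactly 1500 g in the lowest band, whereas the randomisation strata and the SAP put that infant in the middle band. The three places should agree.
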